9.6.2. Efficacy Analysis Methodology

9.6.2.1. Primary Efficacy Endpoint

The primary efficacy endpoint, the proportion of subjects with either a normal 24-hr UFC or a reduction in UFC of $\geq 50\%$ relative to their baseline value at the end of the double-blind randomized withdrawal period, will be evaluated using the Cochran-Mantel-Haenszel (CMH) test, controlling for baseline 24-hr UFC stratum.

Note: the baseline 24-hr UFC is calculated as the mean of all 24-hr UFC levels obtained within the 28 days prior to enrollment into the open-label dose-escalation period.

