3.1.3. Double-blind Randomized Withdrawal Period

The double-blind randomized withdrawal period will be up to 4 weeks in duration. A subject is eligible to enter the double-blind randomized withdrawal period if the mean of the Day 50 and Day 51 (“mean Day 50/51”) 24-hr UFCs meets at least one of the following randomization criteria:

- 24-hr UFC \leq ULN
- 24-hr UFC \leq 50% relative to the baseline value

Eligible subjects will be randomized in a 1:1 ratio to receive either ATR-101 at the same dose level being used at the completion of the open-label dose-escalation period (expected to be 1000 mg BID) or matching placebo. Subjects will continue in the double-blind randomized withdrawal period for 4 weeks or until their mean Day 64/65 24-hr UFC is $> 1.3 \times$ ULN and has also increased by $> 50\%$ relative to their mean Day 50/51 24-hr UFC, whichever comes first. Subjects who are not eligible to be randomized will enter the Additional Open-Label Dosing Period instead of the Double Blind Randomized Withdrawal Period (see below).

- **Study Days 57-70:** Twenty-four-hour UFCs will be collected on Days 64 and 65 (collections start on Days 64 and 65, respectively, and finish on Days 65 and 66, respectively). At the time of Visit R2 (Day 71), if the mean Day 64/65 24-hr UFC result is available and is $> 1.3 \times$ ULN, and has also increased by $> 50\%$ relative to the mean Day 50/51 24-hr UFC, the subject will complete the End-of-Treatment (EoT) visit (Visit R3) instead of Visit R2 and may then be started on another agent at the discretion of his or her physician. Otherwise, the subject will continue in the double-blind, randomized withdrawal period.
- **Study Days 71-85:** Twenty-four-hour UFCs will be collected on Days 79 and 84 (collections start on Days 79 and 84, respectively, and finish on Days 80 and 85, respectively). The EoT visit (Visit R3) will be completed on Day 85. Note: if the mean Day 64/65 24-hr UFC was not available at the time of Visit R2, but subsequently is found to meet criteria for study completion, the EoT visit should be performed as soon as practicable, rather than on Day 85. Additionally, if the Day 79 or Day 84 24-hr UFC is $>$ ULN, after completion of the EoT visit (Visit R3) the subject may begin treatment with another agent at the discretion of his or her physician.

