3.4. Number of Subjects

Approximately 16 subjects are planned to be enrolled in this study. At enrollment, all eligible subjects will be assigned to one of two 24-hr UFC strata. Strata will be assigned according to baseline 24-hr UFC level: 1.3 to $< 4 \times \text{ULN}$ (Stratum I) and 4 to $10 \times \text{ULN}$ (Stratum II). Enrollment into a particular stratum may be limited to ensure the inclusion of subjects in both strata. The subject population will consist of adults with endogenous Cushing's syndrome with 24-hr UFC 1.3 to $10 \times \text{ULN}$.

The study will be conducted at approximately 14 sites in North America and the United Kingdom.

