4.3. Subject Withdrawal Criteria

In accordance with the Declaration of Helsinki and subsequent conferences, subjects have the right to withdraw from the study at any time for any reason. The Investigator and the Sponsor also have the right to withdraw subjects from the study. Subjects may be removed from the study for the following reasons:

1. In the Investigator's judgment, it is in the best interest of the subject to discontinue study participation.
2. The subject experiences an adverse event that would preclude further treatment with the study drug.
3. The subject withdraws consent for continued participation or refuses further treatment with the investigational product.
4. The subject is noncompliant with the protocol.
5. The subject becomes pregnant.
6. The subject cannot tolerate the lowest dose of study drug.

Subjects should return to the study site for an ET visit (which consists of the same procedures as at Visit R3) after withdrawal/removal from the clinical study. The reason for and date of withdrawal/removal from the study must be documented in the subject's medical records.

Investigational site personnel must attempt to determine whether the reason for withdrawal was an AE and if so, this must be reported in accordance with the procedures provided in Section 6.9. For all subjects who do not complete the study, regardless of the duration of treatment, all relevant information related to the withdrawal/removal will be entered into the electronic case report form (eCRF).

Subjects who withdraw or are removed from the clinical study after enrollment into the open-label dose-escalation period will not be replaced. All enrolled subjects will be fully accounted for and documented in the final clinical study reports (CSRs).

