9.2. Sample Size

A sample size of 16 enrolled patients in the open-label dose-escalation period is sufficient per clinical considerations. No formal sample size calculation was performed.

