9.6.2.2. Secondary Efficacy Endpoints

No further adjustments for multiple group comparisons, multiple additional endpoints or multiple subgroups of interest are planned.

Responder analyses and other categorical analyses will be based on the CMH test or Fisher's exact test, as appropriate and if the data allow. Continuous endpoints will be evaluated using ANCOVA or ANOVA model methodology, as appropriate and if the data allow.

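### Must the protocol name an exact version of the CMH test for the primary endpoint, given about 4 subjects or fewer per arm and stratum?

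*Protocol*

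**What the plan says.** Section 9.6.2.1, repeated in the synopsis under Analysis Methodology, states that the primary endpoint "will be evaluated using the Cochran-Mantel-Haenszel (CMH) test, controlling for baseline 24-hr UFC stratum". No exact version, continuity correction or fallback is mentioned.

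Section 9.6.2.2, under the secondary endpoints, is looser: "Responder analyses and other categorical analyses will be based on the CMH test or" Fisher's exact test, where appropriate and where the data permit.

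The size of the comparison follows from several sections:

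- Section 3.4: "Approximately 16 subjects are planned to be enrolled in this study".
- Section 9.2: "A sample size of 16 enrolled patients in the open-label dose-escalation period is sufficient per clinical considerations", and "No formal sample size calculation was performed".
- Section 3.1.3: "A subject is eligible to enter the double-blind randomized withdrawal period if the mean of the Day 50 and Day 51" UFC values meets a response criterion; "Eligible subjects will be randomized in a 1:1 ratio".
- Section 5.8: randomization is stratified by two baseline UFC levels.
- Section 4.3: "Subjects who withdraw or are removed from the clinical study after enrollment into the open-label dose-escalation period will not be replaced".

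Section 9.1, and the synopsis under Statistical Methods, promise a SAP with fuller technical detail, prepared before the double-blind period is unblinded. Only the protocol was available for this review. It states no significance level.

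**The concern.** The chi-square reference distribution for a CMH statistic is a large-sample approximation, and this trial is very small. The same stratified test can be computed with an uncorrected chi-square, with a continuity correction, or from the exact conditional distribution. At this size the three give visibly different p-values, so one outcome may fall on either side of 0.05 depending on the version. The usual software default, uncorrected chi-square, gives the smallest value in the examples worked here.

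The contrast within the protocol adds to the impression. The authors offer an exact test for secondary categorical endpoints, while the sentence on the primary endpoint is unconditional. If the default were anti-conservative, the trial's one primary comparison could be overread.

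**Working it through.** **Inputs.** 16 enrolled (Sections 3.4 and 9.2), two arms at 1:1 (Section 3.1.3), two strata (Section 5.8). The protocol gives no alpha, responder fraction or stratum split. A two-sided 5% level and the layouts below are therefore assumptions. There is no calculated figure in the plan to reproduce.

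**Cell size.** 16 / 2 arms / 2 strata = 4 per cell if everyone is randomized and the strata are equal. This is an average, not a ceiling; uneven strata can give a larger cell.

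**One table by hand.** Take 2 per cell, with all ATR-101 and no placebo subjects responding.

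- Each stratum: observed 2, expected 2 × 2 / 4 = 1, variance 2·2·2·2 / (4²·3) = 1/3.
- Uncorrected: (1 + 1)² / (2/3) = 6.0, p = 0.014.
- Continuity-corrected: (2 − 0.5)² / (2/3) = 3.375, p = 0.066.
- Exact conditional: each stratum has probability 1/6, so 2 × (1/6)² = 0.056.

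A less extreme table with 4 per cell: 4/4 and 3/4 against 1/4 and 1/4.

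- Uncorrected: (1.5 + 1.0)² / (0.536 + 0.571) = 5.65, p = 0.0175.
- Exact: 2 × (5·16 + 5·1 + 30·1) / 4900 = 0.047.

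**All tables.** Among tables with uncorrected CMH p ≤ 0.05:

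| Per cell | Such tables | Exact p > 0.05 | Exact/CMH ratio, range (median) |
|---|---|---|---|
| 4 | 134 of 625 | 56 | 2.23–3.53 (2.72) |
| 3 | 38 of 256 | 20 | 2.71–3.95 (2.99) |
| 2 | 10 of 81 | 10 | 3.36–3.88 (3.36) |

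The difference is therefore real. With 3 per cell, eight further tables have an exact p of exactly 0.05 and are not counted as exceeding it.

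**Which version is off?** A ratio of p-values does not answer this; the true size does. Size is the summed binomial probability, under equal response in both arms, of all tables with p ≤ 0.05. The maximum over one common response rate is:

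| Per cell | Uncorrected CMH | Exact conditional |
|---|---|---|
| 4 | 4.6% | 2.1% |
| 3 | 4.1% | 1.2% |
| 2 | 7.0% | 0% |

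With 3 or 4 per cell the uncorrected test stays below 5%, while the exact test spends less than half of it. About 7.0% is reached in special cases: 2 per cell; a single stratum of 4 against 4; or 4 per cell with stratum response rates of 50% and 0%, where the second stratum carries no information.

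**Price of an exact test.** Power at an assumed 90% against 20% response, two-sided 5%:

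| Layout (per arm) | Uncorrected CMH | Exact conditional |
|---|---|---|
| 3 + 3 | 0.74 | 0.50 |
| 3 + 2 | 0.60 | 0.33 |
| 2 + 2 | 0.66 | 0 |

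With 2 + 2 per arm the smallest attainable exact p is 0.056, so no outcome could be significant. A mid-p version keeps 0.74 at 3 + 3 per arm with a maximum size of 4.1%.

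**The case for a change.** The best case for the concern is that the protocol itself takes up the choice of small-sample test and then offers an exact option only for secondary endpoints. The Mantel-Fleiss rule for trusting the chi-square approximation asks for room of at least 5 on each side of the expected count. With 8 per arm the count spans at most 8, so the rule cannot be met; it fails for all 625, 256 and 81 possible tables at 4, 3 and 2 per cell. Only the exact version is guaranteed to hold its level in every layout, and naming it would take one sentence.

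Much of this stands as fact. The p-value does depend on the version, and the guarantee belongs to the exact test alone. But failing a rule of thumb is a warning, not a demonstrated error; the enumerated size with 3 or 4 per cell is below 5%. Nor does naming the CMH test exclude taking its p-value from the exact distribution. The contrast with the secondary endpoints is weaker than it looks: that sentence is itself unspecific, and in the synopsis it stands as a paragraph of its own covering responder analyses generally. Its place in Section 9.6.2.2 makes that wider reading arguable only, but it does show that sparse tables were foreseen.

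**Conclusion.** The concern does not hold as a criticism of this protocol. The protocol fixes the test and the stratification factor. What it leaves open is the reference distribution, a technical detail that Section 9.1 assigns to a SAP written while the double-blind period is still blinded. Nothing is stated wrongly or contradicted.

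The 2- to 4-fold gap is correct arithmetic, but it mostly measures how conservative the exact conditional test is. With one common response rate, uncorrected CMH has a true size of at most 4.6% with 4 per cell and 4.1% with 3 per cell, rising to about 7% only in special layouts. Requiring the exact test would give up considerable power in a proof-of-concept study (Section 1.4). Uncorrected, mid-p and exact versions are each defensible, and statisticians would reasonably differ.

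This conclusion rests on an assumed two-sided 5% level, on the layouts examined and, for power, on assumed response rates of 90% and 20%. It also rests on the SAP, not seen here, fixing the version before unblinding.

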9.6.2.2. Secondary Efficacy Endpoints

No further adjustments for multiple group comparisons, multiple additional endpoints or multiple subgroups of interest are planned.

Responder analyses and other categorical analyses will be based on the CMH test or Fisher's exact test, as appropriate and if the data allow. Continuous endpoints will be evaluated using ANCOVA or ANOVA model methodology, as appropriate and if the data allow.

9.6.2.3. Exploratory Endpoints

Additional efficacy endpoints may be pre-specified in the Statistical Analysis Plan, including sensitivity analyses associated with drug compliance and missing data issues.

9.7. Safety

9.7.1. Safety Endpoints

Safety endpoints will include the incidence of treatment-emergent adverse events and serious adverse events, as well as changes from baseline in clinical laboratory tests, vital signs, PEs and ECG parameters.

9.7.2. Safety Analyses

Adverse events counts (overall, as well as by severity, causality and seriousness) will be tabulated by Medical Dictionary for Regulatory Activities (MedDRA) system organ class and preferred term. Descriptive statistics and shift tables will be used to summarize continuous laboratory, blood pressure and ECG parameters. Counts and shift tables will be used for categorical lab parameters.

9.8. Pharmacokinetics and Pharmacodynamics

9.8.1. Pharmacokinetic and Pharmacodynamic Endpoints

- The C_{max} , T_{max} , AUC, $t_{1/2}$ and other PK parameters of ATR-101 and its major metabolites (as appropriate and as the data allow)
- The relationship between C_{max} and AUC vs. the percentage change in 24-hr UFC; other PK/PD relationships may be explored as appropriate and as data allow

9.8.2. Pharmacokinetic and Pharmacodynamic Analyses

PK assessments will be performed at each dose level to determine ATR-101 exposures and to profile PK/PD relationships. PK assessments will include C_{max} , AUC_{0-4} and trough levels.

Individual subject PK data will be analyzed along with pooling of subjects' data at each dose level. Individual PK parameters will be derived using the WinNonlin software, and table summaries will be provided using descriptive summary statistics. PK/PD analyses will be detailed in the Statistical Analysis Plan.

9.9. Interim Analysis

No interim analysis is planned for this study.

10. ADMINISTRATIVE CONSIDERATIONS

10.1. Institutional Review Board (IRB)/Ethics Committee (EC)

Prior to initiation of the study at each investigational site, the protocol, the informed consent form(s), the subject information sheet(s), details of the subject recruitment procedures and any other relevant study documentation will be submitted to the responsible local and/or national IRB/EC. A letter from the IRB/EC indicating approval of the Investigator and study site must be submitted to the study Sponsor. All reviews and approval by the IRB/EC will be in accordance with Title 21 of the Code of Federal Regulations (CFR), Part 56. Initial IRB approval and all materials approved by the IRB for this study including the subject consent form and recruitment materials must be maintained by the Investigator and made available for inspection.

The Investigator will promptly report any new information that may adversely affect the safety of subjects or the conduct of the study to the IRB/EC. Similarly, the Investigator will submit written summaries of the study status to the IRB/EC annually, or more frequently if requested. Upon completion of the study, the Investigator will provide the IRB/EC with a brief report of the outcome of the study, if required.

10.2. Ethical Conduct of the Study

The guidelines of the World Medical Association Declaration of Helsinki in its revised edition (48th General Assembly, Somerset West, Republic of South Africa, October 1996), the guidelines of ICH GCP (CPMP/ICH/135/95), as well as the demands of national drug and data protection laws and other applicable regulatory requirements, will be strictly followed.

10.3. Subject Information and Consent

The Investigator is responsible for ensuring that subjects do not undergo any study-related examination or activity before giving informed consent. The subject must give written consent after the receipt of detailed information regarding the study. The verbal explanation will cover all the elements specified in the written information provided to the subject. If the written informed consent is provided by the legal guardian because the subject is unable to do so, a written or verbal assent from the subject must also be obtained.

The Investigator will inform the subject of the aims, methods, anticipated benefits and potential hazards of the study, including any discomfort it may entail. The subject must be given every opportunity to clarify any points he/she does not understand and must be provided with more information if requested. At the end of the interview, the subject may be given time to reflect and can request more time if needed. The subject and/or legal guardian will be required to sign and date the informed consent form. After completion, informed consent forms will be kept and archived by the Investigator in the Investigator study file.

It should be emphasized to the subject that he or she is at liberty to either discontinue study drug and/or withdraw consent to participate at any time, without penalty or loss of benefits to which he or she is otherwise entitled. Subjects who refuse to give or withdraw written informed consent may not be included or continued in this study, but this will not affect their subsequent care.

Please refer to Title 21 of the CFR, Part 50 – Protection of Human Subjects for specific details on this regulation.

10.4. Subject Confidentiality

Personal and sensitive data will be treated as confidential. The results of the study will be made available for review by authorized representatives of the Sponsor and/or submitted to the IRB/EC and regulatory authorities.

Prior to any screening procedures being performed, the subject's consent is required for the data to be used for these purposes and to gain direct access to their medical records for data verification purposes. The subject must be assured that their identity will be protected. To facilitate this, a unique identification number will be assigned and it will be used when reporting study-related data.

Additionally, in the US, the Health Insurance Portability and Accountability Act of 1996 ("HIPAA") requires that all subjects grant permission to use their personal health information. Therefore, in addition to the protocol-specific ICF, each subject located in the United States (US) will be asked to provide authorization to use his/her personal health information by signing a separate HIPAA Authorization Form.

10.5. Study Monitoring

It is understood that the Sponsor or its designee (e.g., the CRA) will contact and visit the Investigator regularly for monitoring purposes. The CRA will be allowed, on request, to inspect the various records of the study (i.e., eCRFs, source documents and any other pertinent data), provided that subject confidentiality is maintained in accordance with local requirements. It will be the CRA's responsibility to inspect the eCRFs at regular intervals throughout the study, to verify adherence to the protocol and to ensure the completeness, consistency and accuracy of the data entered. The CRA must have access to all subject records needed to verify the entries on the eCRF. The Investigator agrees to cooperate with the CRA to ensure that problems detected during these monitoring visits are resolved.

Before an investigational site can consent a subject into the study, a representative of Millendo Therapeutics, Inc. will evaluate the investigational study site to assess the site including but not limited to:

- Determine the adequacy of the facilities including the site's ability to carry out the protocol
- Discuss with the Investigator(s) and other personnel their responsibilities with regard to protocol adherence and the responsibilities of Millendo Therapeutics, Inc. or its representatives. This will also be documented in a Clinical Study Agreement between Millendo Therapeutics, Inc. and the Investigator.

During the study, a monitor from Millendo Therapeutics, Inc. or representative will have regular contacts with the investigational site, for the following but not limited to:

- Provide information and support to the Investigator(s)
- Confirm that facilities remain acceptable
- Confirm that the investigational team is adhering to the protocol, that data are being accurately recorded in the case report forms and that investigational product accountability checks are being performed

- Perform source data verification. This includes a comparison of the data in the case report forms with the subject's medical records at the hospital or practice and other records relevant to the study. This will require direct access to all original records for each subject (e.g. clinic charts).
- Record and report any protocol deviations not previously sent to Millendo Therapeutics, Inc.
- Confirm AEs and SAEs have been properly documented on CRFs and confirm any SAEs have been forwarded to Millendo Therapeutics, Inc. and those SAEs that met criteria for reporting have been forwarded to the IRB.

The monitor will be available between visits if the Investigator(s) or other staff needs information or advice.

10.6. Audits and Inspections

Authorized representatives of Millendo Therapeutics, Inc., a regulatory authority, an Ethics Committee or an Institutional Review Board may visit the site to perform audits or inspections, including source data verification. Millendo Therapeutics, Inc. may perform Clinical Quality Assurance (CQA) audit randomly at a sample of clinical sites, or for cause as warranted. The purpose of a Millendo Therapeutics, Inc. CQA audit or inspection is to systematically and independently examine all study-related activities and documents to determine whether these activities were conducted and data were recorded, analyzed and accurately reported according to the protocol, GCP guidelines of the ICH and any applicable regulatory requirements. These audits will be independent of routine monitoring by the CRA and initiated with prior written notification provided to the site.

The Investigator should contact Millendo Therapeutics, Inc. immediately if contacted by a regulatory agency about an inspection.

